Study Title: Estrogen mediated vascular endothelial dysfunction in Diabetes Brief Title: Estrogen and Diabetes Clinical Trials: NCT03436992 Document Version Date: 11.14.22 Principal Investigator: [name]

1. Objectives

Describe the purpose, specific aims, and hypothesis:

The purpose of this proposal is to investigate whether or not estrogen contributes to vascular dysfunction in premenopausal women with diabetes. Specific Aim 1. To test the hypothesis that estrogen contributes to vascular endothelial dysfunction in premenopausal women with diabetes.

2. Background

Describe the background and rationale for the study:

There is an extensive body of knowledge that indicates premenopausal women have an innate protection from cardiovascular disease and estrogen is what contributes to this protection. In contrast to these protective findings in humans, using an animal model, estrogen in diabetes has been indicated to contribute to vasoconstriction.

3. Inclusion and Exclusion Criteria

List the inclusion/exclusion criteria: Inclusion criteria:

- Both boys/men (with T1DM) and girls/premenopausal women (with or without T1DM)
- \geq 7 years of age
- Normal menstrual cycle interval of 25-35 days for at least 3 previous cycles
- All races
- Clinical diagnosis of insulin-dependent type 1 diabetes (patients only)

Exclusion criteria:

- Clinical diagnosis of hepatic, cardiovascular, or renal disease
- Uncontrolled Diabetes (HbA1c > 12%)
- Diabetic complications (i.e. macrovascular, microvascular, or autonomic)
- Proteinuria
- Uncontrolled Hypertension (>140/90 mm Hg on therapy)
- Pregnancy
- Oligomenorrhea
- Direct vasoactive medications (i.e. nitrates)
- Anti-estrogens (i.e. SERMs)
- Polycystic ovarian syndrome (defined by NIH guidelines hyperandrogenic anovulation)
- Undetectable Anti-Mullerian Hormone (AMH) following screening

4. Number of Subjects/Records/Samples Collected

Indicate the total number of subjects to be accrued/records reviewed/samples collected across all sites: 198 total subjects to be accrued

5. Recruitment Methods

Describe when, where, and how potential subjects will be recruited:

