• Arterial Function (FMD) - Measurements of arterial health will be completed using ultrasound technology to detect how well the artery expands with changes in blood flow. This technique is used to characterize the health of arteries. The subject will lie down for 20 minutes to become fully rested. After the 20 minute resting phase, a water based gel will be put on the ultrasound transducer and then put on the subject's skin. The gel helps achieve better pictures of the artery. We will then test the artery function. After baseline measurements, a blood pressure cuff placed around the forearm will be inflated to 250 mm Hg to stop blood flow for 5 minutes. Data will be recorded for 2 minutes following the

release of the cuff. The health of the artery will be expressed as a percentage of the artery expansion with the increased blood flow, compared to the resting diameter.

• Nitroglycerin spray (EID) – Nitroglycerin is a fast acting drug that causes blood vessels to dilate (or get bigger). After we perform the post FMD test and while the subject is still laying down, [name] or his research associate will spray one dose (0.4 mg/spray) of nitroglycerin under the tongue. We will continue to monitor heart rate, blood pressure, and the blood vessel through ultrasound for up to 15 minutes. This test measures arterial health and the maximal capability of the artery to expand.

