• Continuous Glucose Monitoring (CGM) -- For patients that use a Dexcom for clinical evaluation of continuous glucose monitoring, we will ask him/her for permission to share their data using the Clarity software provided by Dexcom. To do this, we will send them a link that integrates

their individual continuous glucose data with the Clarity software to give us real time access of the data throughout the duration of the study. The Clarity software is HIPAA compliant, and patients using this software have already agreed to share their health information with Dexcom. Our study team will discontinue our access to the patient's data through the Dexcom Clarity app within one week of the participant's final visit. This will remove all future access to the participant's data. Access can only be granted if the participant re-shares their data with our research team.

• Randomized Treatments – After enrollment, the subject will be randomized to receive either an antioxidant cocktail, resveratrol, or a placebo. The antioxidant cocktail is comprised of over the counter vitamins (vitamin C 1,000 mg, vitamin E 600 IU, and alpha lipoic acid 600 mg) that will be given in two doses, 30 minutes apart. Resveratrol (1500 mg of trans-resveratrol) is a natural polyphenol that is found in multiple food sources. Nicotinamide riboside (1,000 mg) is an over-the-counter supplement. The placebo will consist of lactose or sucrose (sugar pills).

b. Describe and explain the study design:

Brachial artery flow-mediated dilation and a small blood sample (10 ml) will be performed in the girls/women during the menses (days 1-5 of the menstrual cycle) and late follicular (day 12-14) phases, whereas the men will be studied twice at the same frequency as the girls/women. Participant subject medical information will be assessed during the first visit.

c. Describe the procedures performed to lessen the probability or magnitude of risks:

All procedures in this study have been routinely performed in research studies in the past and are of low risk to participants. [name] is a trained clinical exercise physiologist with experience performing high-risk exercise in patient populations. In an effort to maintain subject safety but also investigate endothelial dysfunction from smooth muscle dysfunction, we will administer nitroglycerin only in adults, and only one time at baseline.

d. Describe the duration of an individual subject's participation in the study and the time involved:

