Participation in the study will involve 3 testing visits to the GPI (one preliminary testing visit at the beginning of the study and 2 experimental that for females are based on their menstrual cycle. Prelim visit will take approximately 2 hours, experimental visits 1 and 2 will last approximately 5 hours. Those subjects serving as controls will not receive randomized treatments. Participants may or may not be asked to conduct all visits or even take treatments and/or perform all procedures during each experimental testing day depending on time and availability. If a subject recently participated in a study with us that involved these same tests, we may use data from that study to avoid redundant testing measures.

7. Data and Specimen Management

Thi gen	cribe the data analysis plan, including any statistical procedures: s is simply a pilot experimental study. Therefore, descriptive statistics will be erated and paired t-tests and linear regression analyses will be performed ong the dependent variables; FMD, hormones, and lipids.	□ N/A			
b. Wh	en applicable, provide a power analysis:	□ N/A			
	re is no formal power calculation because this proposal is designed just btain preliminary data for a grant submission.				
c. Des	cribe how data and specimens will be handled:	□ N/A			
i.	What information will be included in that data or associated with the specin	mens?			
	All data sheets and stored specimens will be de-identified.				
ii.	Where and how data and/or specimens will be stored?				
	Data are stored in subject folders, specimens are stored de-identified in -80) freezers			
iii.	How long will the data and/or specimens be stored?				
	Click here to enter text.				
iv.	Who will have access to the data or specimens?				
	Only investigators that will be involved with the data will have access to the specimens	e data or			
V.	Who is responsible for receipt or transmission of the data and/or speciment	s?			
	[name] is responsible				
vi	How will data and/or specimens be transported?				
	Specimens will be transported according to the biosafety procedures and				
	regulations				

8. Provisions to Monitor the Data to Ensure the Safety of Subjects

This study involves no more than minimal risk study and this section is not required. \Box N/A

The plan might include establishing a data monitoring committee and a plan for reporting data monitoring committee findings to the IRB and the sponsor.

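### Does stating FMD only as a percentage of resting diameter leave the comparison between menstrual phases open to a hidden shift in resting diameter?

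*Combined protocol and SAP*

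**What the plan says.** Under Arterial Function (FMD) in Section 6a, resting measurements come before occlusion: "After baseline measurements, a blood pressure cuff placed around the forearm will be inflated". The result is then "expressed as a percentage of the artery expansion with the increased blood flow, compared to the resting diameter". No other FMD scale is given.

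Section 6b sets the contrast within each female participant: "Brachial artery flow-mediated dilation and a small blood sample (10 ml) will be performed in the girls/women during the menses" and again in the late follicular phase.

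The analysis plan in Section 7a is very short. It calls the work "simply a pilot experimental study", promises descriptive statistics, and says that "paired t-tests and linear regression analyses will be performed" among the "dependent variables; FMD, hormones, and lipids". Resting diameter, peak diameter and dilation in mm are not named. Section 7b says there is no formal power calculation, because the purpose is preliminary data for a grant application.

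On nitroglycerin, Section 6c says "we will administer nitroglycerin only in adults, and only one time at baseline".

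**The concern.** A percentage change can move through its numerator or its denominator. The exposure under study, estrogen, is what differs between the two visits, and the Background itself raises an effect on vascular tone: "using an animal model, estrogen in diabetes has been indicated to contribute to vasoconstriction". If estrogen altered the resting brachial artery, FMD% could change although the artery dilated by the same number of millimetres.

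The usual safeguards do not help. Pairing removes stable differences between women, but not a change in the same woman between visits. The nitroglycerin test is given once and only to adults, so it gives no comparison between phases.

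Specific Aim 1 concerns endothelial dysfunction. A larger resting artery at the late follicular visit could look like a small loss of function, and a smaller one could hide a loss. A reader who saw only FMD% could not tell these apart.

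**Working it through.** The plan has no figure to reproduce. It gives no diameters, FMD values, standard deviations or power calculation. The 198 subjects in Section 4 are not split by group. All inputs below except the 198 are therefore assumptions.

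**Definition (from Section 6a).** FMD% = 100 × (peak − rest) / rest. Let f be the starting FMD% and c the proportional change in resting diameter.

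**Case 1: dilation in mm unchanged.** The shift is f/(1 − c) − f for a smaller artery and f/(1 + c) − f for a larger one. With f = 6%:

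| c | Smaller artery (points) | Larger artery (points) |
|---|---|---|
| 1% | +0.06 | −0.06 |
| 2% | +0.12 | −0.12 |
| 3% | +0.19 | −0.17 |
| 5% | +0.32 | −0.29 |

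At c = 3%, f = 4% gives +0.12 and −0.12, and f = 8% gives +0.25 and −0.23.

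**Case 2: dilation proportional to resting diameter.** Numerator and denominator move together, so the shift is 0.

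**Case 3: peak diameter fixed.** The shift is (100 + f)/(1 ∓ c) − (100 + f). With f = 6%:
- c = 1%: 106/0.99 − 106 = +1.07; 106/1.01 − 106 = −1.05.
- c = 3%: 106/0.97 − 106 = +3.28; 106/1.03 − 106 = −3.09.

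This is a boundary case. With 3.500 mm at rest and a peak of 3.710 mm, a 3% larger resting artery (3.605 mm) would dilate by only 3.710 − 3.605 = 0.105 mm, half of the starting 0.210 mm. Dilation in mm would move as well, so a change of scale would not remove the ambiguity.

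**The ambiguity itself.** Start at 3.500 mm and 0.210 mm, which is 6.00%. A later reading of 5.83% fits a 3% larger artery with the same dilation (0.210/3.605). It also fits an unchanged artery dilating 0.204 mm, which is 2.9% less. FMD% alone does not separate them.

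**Effect on a real loss.** Suppose dilation in mm falls by 10%, so that FMD would be 5.40% with the resting artery unchanged. A 3% smaller artery reads 5.40/0.97 = 5.57%, and a 3% larger one reads 5.40/1.03 = 5.24%. The observed falls are 0.43 and 0.76 points against 0.60. The size changes but the direction does not.

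**Scale against sampling error.** The 95% CI half-width for a paired mean is t(0.975, n − 1) × SD/√n. Assume an SD of 1 to 3 points for the within-woman change in FMD:
- n = 20: 2.093 × SD/4.472 = 0.47 to 1.40 points.
- n = 50: 2.010 × SD/7.071 = 0.28 to 0.85 points.

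The 0.17-point shift in the example lies inside these widths. That would not hold at every sample size. If all 198 subjects were paired women, an SD of 1 point would give 1.972 × 1/14.07 = 0.14. The 198 include men and healthy controls, so the group that Aim 1 concerns is smaller.

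**The case for a change.** The strongest argument for acting is cost. The scans already exist, the paired t-test is already planned, and two sentences in Section 7a would commit the team to reporting resting diameter, peak diameter and their difference. A pilot meant to support a grant would gain from knowing how far resting diameter moves between phases. The documents also give no basis for choosing among the three cases, so the large shifts cannot be ruled out from the text. The skin blood flow tests in Section 6a do not use a brachial diameter, but they are no sure substitute: Section 7a does not list them, and Section 6d allows procedures to be skipped.

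Much of this stands. Reporting the diameters would be good practice and cheap. It does not show an error in the plan, for three reasons.

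- FMD% would remain the main measure with the same test and the same result. The addition is exploratory description with no decision rule, and it cannot settle whether percent or millimetres is the right scale.
- Its precision would be limited. With an assumed SD of 2% to 5% for the within-woman change in resting diameter, the 95% CI half-width is 0.9% to 2.3% at 20 pairs and 0.6% to 1.4% at 50. Over much of that range a 1% shift could not be excluded.
- Nothing in the documents indicates that resting brachial diameter changes between phases. The animal finding in the Background does not address it.

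**Conclusion.** No change to the plan follows. The stated analysis does not cover a change in resting diameter between phases, and such a change could shift FMD%. This is a general property of a percentage outcome, and the analysts can deal with it when they report. They must hold the resting diameter and the dilation behind every FMD value, Section 7a already promises descriptive statistics, and a short pilot plan that does not name a component has not decided to ignore it. Because Section 6a describes blood sampling before and after treatment on each experimental day, such a description would naturally use the pre-treatment scans, so that phase is not mixed with treatment.

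On the assumed inputs (FMD of 6%, dilation in mm unchanged, resting diameter 1% to 5% different), the shift is about 0.06 to 0.32 points. It is zero under proportional dilation and reaches 1 to 3 points for a 1% to 3% change only with a fixed peak. Specific Aim 1 does not itself name FMD%, and Section 7 presents no confirmatory test. The documents do not show that following the plan as written would lead to a wrong conclusion.

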• Blood Sample - Blood samples will be taken from a vein by the P.I., phlebotomist, or research assistant that is certified in drawing blood. At the preliminary visit, up to 18 ml of blood (approximately 1-2 tablespoons) will be taken to test for blood counts, the amount of sugar in the blood and certain hormones. For **ADULTS**: Up to 75 ml of blood (approximately 4 - 5 tablespoons) will be taken during each experimental day (approximately 44 ml pre- treatment and 31 ml post-treatment). This amount is less than 1/5 of the amount that is withdrawn during a normal blood donation (500 ml or 15 fluid ounces). For **CHILDREN**: Up to 50 ml of blood (approximately 3 – 4 tablespoons) will be taken during each experiment and 20 ml post-treatment). This amount is about 1/10 of the amount that is withdrawn during a normal blood donation (500 ml or 15 fluid ounces). To prevent the number of needle sticks for the blood draws, a sterile plastic catheter tube will be placed for the duration of experimental day 2. We will use this blood to test for blood fat (cholesterol), blood sugar, and the concentration of certain hormones. **NOTE**: Healthy controls will not receive treatment, and therefore the blood draw amount will be the "pre-treatment" volume listed above.

• Arterial Stiffness Evaluation (PWV/PWA) – A device will be used to measure how fast blood travels. This test is called pulse wave velocity or PWV. How fast blood travels is also a measure of how stiff the arteries are. Stiff blood vessels/arteries are linked to high blood pressure and heart disease. To start the test, a blood pressure cuff is placed on the subject's arm and leg. A pen-like device is gently applied on the carotid artery (neck) and the radial artery (wrist) to record how fast the blood flows between each of the points.

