Treatments: There are occasional side effects associated with ingestion of the antioxidant cocktail and Resveratrol that include nausea, upset stomach and diarrhea. These side effects are more common with higher doses. Risks for the antioxidants used in this study will be minimized by not exceeding the recommended dosing. Possible side effects of nicotinamide riboside are typically mild and may include skin flushing, hypotension, nausea, and bloating.

Reproductive Risks: Being a part of this study while pregnant may expose the unborn child to potential risks, some of which may be currently unforeseeable. Therefore, pregnant women will be excluded from the study. If the participant is a girl/woman of childbearing potential, a pregnancy test will be done and it must be negative before she can continue in this study.

If sexually active, the participant must agree to use appropriate contraceptive measures for the duration of the study. Medically acceptable contraceptives include:

- 1. surgical sterilization (such as a tubal ligation) [ADULTS ONLY]
- 2. approved hormonal contraceptives (such as birth control pills or patches),
- 3. barrier methods (such as a condom or diaphragm) used with a spermicide, or
- *4. a copper intrauterine device (IUD).*

If the participant does become pregnant during this study, she should inform the study staff immediately.

If applicable, describe any costs that subjects may be responsible for because of participation in the research. No cost other than transportation to the GPI.	⊠ N/A
If applicable, describe risks to others who are not subjects.	x N/A
	because of participation in the research. No cost other than transportation to the GPI.

11. Potential Benefits to Subjects

Describe the potential benefits that individual subjects may experience from taking part in the research. Although there is no direct benefit to the participant, access to the results and information on blood lab values, blood pressure, and the functional and structural measurements of the health of the participants' arteries will be available. They may also choose whether they receive the results of these assessments; however, if the participant choose to receive the results, [name] or another qualified research member will explain the results to the participant in detail.

12. Confidentiality

Describe the procedures for maintenance of confidentiality.

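### Oral amounts are fixed from age 7 upward, and no rule limits them to children whom an age-appropriate recommendation covers; on assumed weights the youngest boys get about 2–4 times the adult amount per kg

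*Combined protocol and SAP*

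**What the plan says.** Section 6a, Randomized Treatments: "After enrollment, the subject will be randomized to receive either an antioxidant cocktail, resveratrol, or a placebo". No age restriction follows. The cocktail is "vitamin C 1,000 mg, vitamin E 600 IU, and alpha lipoic acid 600 mg) that will be given in two doses, 30 minutes apart". The other randomized active product is "Resveratrol (1500 mg of trans-resveratrol"). The same paragraph lists nicotinamide riboside at 1,000 mg, although not among the randomized options. None of these amounts comes with a per-kg rule, age band, minimum weight or cap.

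Section 3 sets the minimum age at 7 and admits "Both boys/men (with T1DM) and girls/premenopausal women (with or without T1DM"). It also asks for "Normal menstrual cycle interval of 25-35 days for at least 3 previous cycles", which in practice means that girls must be past menarche.

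Section 6a, Blood Sample, allows adults "Up to 75 ml of blood" per experimental day and children up to 50 ml, with a 20 ml post-treatment draw in the children's text. Section 6c restricts nitroglycerin to adults. Section 6d exempts controls from randomized treatment and says that others may skip treatments or procedures depending on time and availability.

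Section 10a, Treatments, lists occasional nausea, upset stomach and diarrhea for the cocktail and resveratrol. It continues: "These side effects are more common with higher doses" and "Risks for the antioxidants used in this study will be minimized by not exceeding the recommended dosing".

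**The concern.** The protocol sets child-specific limits for two other procedures (blood volume and nitroglycerin) but gives a 7-year-old boy the same oral amount as an adult man. It also acknowledges that side effects increase with dose. The only safeguard that governs the dose is the reference to recommended dosing. If that recommendation was written for adults, it does not protect the lightest participants. If it covers children, nothing in the protocol makes that coverage a condition of being dosed. At stake is the safety of a small child given a single-day oral load, and whether the stated safeguard applies to that child at all.

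**Working it through.** The documents give no body weights and no dose per kg, so there is no plan figure to reproduce.

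**Inputs from the protocol (Section 6a).** Resveratrol 1,500 mg; vitamin C 1,000 mg; alpha lipoic acid 600 mg.

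**Assumed inputs (not in the documents).** Youngest boys 20–30 kg; larger children 35–40 kg; a girl past menarche 45 kg; adults 60–80 kg.

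**Formula.** For a fixed amount D,

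ratio = (D / child kg) ÷ (D / adult kg) = adult kg / child kg.

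D cancels, so the ratio is the same for every product.

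**Ratios.**

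| Comparison | Calculation | Ratio |
|---|---|---|
| Youngest boys, low end | 60 / 30 | 2.0 |
| Youngest boys, high end | 80 / 20 | 4.0 |
| Intermediate case | 70 / 23 | 3.0 |
| Larger child, 35 kg | 60 / 35 | 1.7 |
| Larger child, 40 kg | 60 / 40 | 1.5 |
| Girl of 45 kg | 60 / 45 to 80 / 45 | 1.3 to 1.8 |
| Adults against each other | 80 / 60 | 1.3 |

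All adult weights here lie in the same 60–80 kg range. The girl's ratio starts at the spread among adults and runs above it, but stays below the range for the youngest boys.

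**Amounts per kg.**

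| Product | 20 kg | 30 kg | 60 kg | 80 kg |
|---|---|---|---|---|
| Resveratrol 1,500 mg | 75 | 50 | 25 | 18.8 |
| Vitamin C 1,000 mg | 50 | 33.3 | 16.7 | 12.5 |
| Alpha lipoic acid 600 mg | 30 | 20 | 10 | 7.5 |

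The cocktail is given in two doses, and the text can be read as listing totals or amounts per administration. If per administration, every cocktail figure doubles (alpha lipoic acid 60 and 40 mg/kg at 20 and 30 kg). The ratios do not change. This is why the rule below refers to the total amount given.

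**Can a child actually be dosed?** Eligibility from age 7 (Section 3), randomization of the subject without an age limit (Section 6a), exemption of controls only (Section 6d), and a post-treatment draw for children (Section 6a) together say yes.

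**The case against.** The strongest objection is that no fault in dosing has been demonstrated. More mg per kg is not in itself more risk. The documents give no pharmacokinetics and no paediatric limit, and the recommended dosing in Section 10a may well be age-appropriate. That stands: a reader might infer that children are overdosed, and the documents do not support it.

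The 4.0 pairs the lightest assumed child with the heaviest assumed adult, and larger children come out at 1.5–1.7. That stands too, and is why a range is given.

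Sections 8 and 9 provide continuous vital signs, stopping on significant change, review at each visit, cover by a study physician, and withdrawal if harm is suspected. The listed side effects of the cocktail and resveratrol are gastrointestinal and occasional. These points lower the likely severity. They do not answer the concern, because monitoring reacts to an event and does not set a dose.

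The comparison with other child limits has limits of its own. Nitroglycerin carries more marked risks in Section 10a (headache in about half, hypotension, passing out). The blood cap is not scaled to weight either: 50 ml at 20 kg is 2.5 ml/kg, against about 1.1 ml/kg for 75 ml at 70 kg. The contrast shows only that the protocol considers age elsewhere.

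It may be said that Section 6d already allows a child to go untreated. It does so for time and availability, not for age or weight.

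A reader might also infer that varying dose per kg biases a comparison of arms. Section 7 describes a pilot with descriptive statistics, paired t-tests and regression, and states no comparison of arms. No analysis change is warranted on this ground.

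**Conclusion.** The point holds as a matter of patient safety. One fixed oral amount applies to every randomized subject from age 7, and the only safeguard on dose is not tied to an age group. On assumed weights the youngest boys would receive about 2–4 times the adult amount per kg, falling to about 1.5–1.7 times for a 35–40 kg child against a 60 kg adult. The ratio rests entirely on those weights. The protocol does not say how many young boys are expected, and does not show that any child has yet been dosed. No harm and no exceeded limit is claimed. It is a cheap improvement to conduct and does not put the study's results in question.

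**What to change.** Add a rule to Section 6a, Randomized Treatments, applied before randomisation: a child receives an oral product only if the study physician confirms that the total amount given is within a recommendation covering that child's age or weight. For this to work before allocation, the confirmation has to cover every product to which the child could be assigned. Children who do not meet the rule are not randomised and are tested without treatment, in the same way that Section 6c already limits nitroglycerin to adults. This must be written as a new rule, because Section 6d does not permit omission on grounds of age or weight. Applying it before allocation avoids removing children after they have been assigned. This review proposes no dose.

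The cost is a short amendment and one physician confirmation per child. Weight is already measured for BMI (Section 6a, Body Composition), so no new measurement is needed. The downside is that some children leave the treated group.

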Subjects will be recruited through word of mouth and flyer placement. Word of mouth recruitment will take place through ordinary interactions by the principal and sub-investigators with individuals in the community and in clinic. Once informed of the study, individuals will be asked to call [name] or [name] at the GPI if interested in participating. The telephone screening form will be used for when subjects contact the GPI to verify eligibility prior to the consent visit. If the subject chooses not to enroll in the study during that time, the telephone screening form (with any PHI) will be shredded.

The current study will NOT recruit vulnerable participants whom include: fetuses, pregnant women, human in vitro fertilization, prisoners, or other institutionalized individuals. MCG employees who wish to participate may only do so if they are not on the protocol or working for any investigators listed on the protocol.

6. Procedures Involved

a. Describe the procedures involved to include those procedures that are standard evaluation and/or care and those that are solely for research purposes:

• Blood Pressure – Standard non-invasive blood pressure techniques will be used to measure subject's blood pressure. Participants will be asked to sign a consent form to obtain blood pressure measurements prior to reviewing the study consent document.

• Questionnaires- Participants will be asked to fill out a questionnaire to gather contact information, personal information, and family and health history. The health history questionnaire will ask questions about family history of certain medical conditions, current medications, heart disease, and the type(s) of exercise performed.

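### Eligibility does not address participants' own use of the over-the-counter agents being randomised, so current users can enter any arm and the treatment response can be attenuated

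*Combined protocol and SAP*

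**What the plan says.** All references are to the combined protocol and SAP.

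- **Arms (Section 6a, Randomized Treatments).** After enrolment "the subject will be randomized to receive either an antioxidant cocktail, resveratrol, or a placebo". The cocktail components are called over the counter: "The antioxidant cocktail is comprised of over the counter vitamins (vitamin C 1,000 mg, vitamin E 600 IU, and alpha lipoic acid 600 mg". Resveratrol is described as occurring in foods. The same paragraph adds "Nicotinamide riboside (1,000 mg) is an over-the-counter supplement", but the sentence listing the arms does not include that agent.
- **Eligibility (Section 3).** The medication exclusions are "Direct vasoactive medications (i.e. nitrates") and "Anti-estrogens (i.e. SERMs"). Nothing covers vitamin C, vitamin E, alpha lipoic acid or resveratrol, and there is no washout.
- **What is recorded (Section 6a, Questionnaires).** The health history form asks about "family history of certain medical conditions, current medications, heart disease, and the type(s) of exercise performed". Supplements are not named, and the answers are not tied to eligibility or analysis. Section 5 adds a telephone screen to verify eligibility.
- **Risk statement (Section 10a, Treatments).** "Risks for the antioxidants used in this study will be minimized by not exceeding the recommended dosing". No limit is given, and a participant's own intake is not mentioned.
- **Analysis (Section 7).** Descriptive statistics, paired t-tests and linear regression, in a pilot with no formal power calculation.

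**The concern.** Section 3 keeps out drugs that act directly on vessels and drugs that oppose estrogen, because either would disturb what the study measures. The agents randomised in order to change vascular function get no such treatment, although anyone can buy the cocktail components.

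Followed as written, a woman who takes vitamins C and E daily can be assigned to placebo and counted as unexposed, or assigned to the cocktail with a pre-treatment value that may already reflect part of its effect. In either case the estimated response can be smaller than in non-users. Because the plan does not ask about supplements by name, the sponsor might be unable to tell an absent effect from prior supplementation. The data are meant as preliminary evidence for a grant submission, so an attenuated estimate would carry forward.

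**Working it through.** **Plan's own figure.** There is none to reproduce. Section 4 gives 198 participants in total; Section 7 gives no alpha, power, effect size, SD or allocation ratio.

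**Text check.** No section excludes, washes out, stratifies on or adjusts for own use of the randomised agents.

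**Attenuation.** Let D be the true effect in non-users, u the fraction already taking the assigned agent, s the share of D lost in a user, k the amount by which a user's baseline is already shifted, and B a non-user's baseline.

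- Pre-to-post change: the active arm changes on average by (1 - u)D + u(1 - s)D = (1 - us)D. The placebo arm changes by 0, users and non-users alike. The difference is (1 - us)D.
- Post-treatment values only: the active arm averages (1 - u)(B + D) + u(B + k + (1 - s)D) and the placebo arm averages B + uk. The difference is again (1 - us)D.
- Pre-to-post change within one active arm, by paired t-test: (1 - us)D.

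The same factor applies whichever analysis is used; the routes do not add up. With s = 1 it is (1 - u): 90% of D at u = 0.10, 80% at 0.20, 70% at 0.30. With s = 0 there is no loss.

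**What that could cost, for illustration only.** Assumptions: two-sided alpha 0.05, equal arms, unchanged SD, and 80% power when nobody uses the agents. Taking 198/3 = 66 per arm is an upper bound, because controls are not randomised (Section 6d). The detectable standardised difference is (1.96 + 0.84) × √(2/66) = 0.49. Power under attenuation is Φ(0.488 × (1 - us) × √(66/2) - 1.96), and the sample size to restore 80% rises by 1/(1 - us)².

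| u | s | effect kept | power | sample-size factor | n per arm for 80% |
|---|---|---|---|---|---|
| 0 | any | 1.00 | 80% | 1.00 | 66 |
| 0.10 | 0.5 | 0.95 | 76% | 1.11 | 74 |
| 0.10 | 1 | 0.90 | 71% | 1.23 | 82 |
| 0.20 | 0.5 | 0.90 | 71% | 1.23 | 82 |
| 0.20 | 1 | 0.80 | 61% | 1.56 | 104 |
| 0.30 | 0.5 | 0.85 | 66% | 1.38 | 92 |
| 0.30 | 1 | 0.70 | 50% | 2.04 | 135 |

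At 33 per arm the detectable difference is 0.69 and the proportional losses are the same.

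**Menstrual-phase comparison.** Section 6b measures each female participant at menses and again in the late follicular phase. A constant shift k is present at both and drops out of the within-person difference, as long as use is steady and its effect is similar in the two phases.

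**The case against.** The strongest reply is that the only Specific Aim concerns estrogen, that the design compares phases within a person, and that Section 7 names no active-versus-placebo test. That is correct, and it limits the point: the affected contrast follows from the randomisation and from the pre- and post-treatment sampling in Section 6a. The point does not disappear, because a paired pre-to-post change in an active arm is attenuated by the same factor.

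Randomisation also balances users across arms in expectation. This is therefore attenuation and added variability, not confounding. In addition, u counts only users of the assigned agent: a vitamin C user assigned to resveratrol, or to a three-component cocktail, is not thereby a non-responder.

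The forms themselves are not in the documents, and they may ask about supplements. Even so, the protocol gives such an answer no consequence.

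Two stronger readings are tempting:

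- A reader might infer that own use plus study supply breaks the Section 10a statement on recommended dosing. The documents do not show this. The statement concerns the antioxidants used in the study, gives no limit, and no participant's intake is known. What can be said is that total intake is not addressed.
- A reader might infer that a false finding of no antioxidant effect is to be expected. That would need a prevalence of use and a residual response, and the documents give neither.

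**Conclusion.** The gap is real: eligibility is silent on own use of the randomised agents, and a current user can be assigned to any arm. The consequence is possible attenuation of the treatment response by the factor (1 - us), which becomes (1 - u) when users have no further response. Over the assumed range (u up to 0.30, s from 0 to 1), the loss runs from nothing to 30% of the effect. These inputs are assumptions and no figure in the plan changes.

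The menstrual-phase comparison that serves the Specific Aim is largely unaffected by steady use. Since this is a pilot without a power calculation, the point is an inexpensive improvement that protects the randomised part of the study. It does not invalidate the design.

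**What to change.** - **Section 3:** for participants who will be randomised, add an exclusion or washout for regular supplement use of the randomised agents, with the period set by the sponsor. Controls receive no treatment, so the reason given here does not extend to them.
- **Sections 5 and 6a:** ask about supplements by name on the existing telephone screen and health questionnaire, and again at each experimental visit.
- **Section 7:** where users have already been enrolled, include use as a covariate in the planned linear regression. A main-effect covariate adjusts for a difference in level but does not restore a blunted response, so also describe the response separately by use.
- **Section 6a, Randomized Treatments:** reconcile the description of nicotinamide riboside with the sentence that lists the arms, so that it is clear which agents the new criterion covers.
- **Section 10a, Treatments:** state whether the dosing statement refers to study supply only or to total intake.

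The cost is one eligibility line, one question on forms already in use, and slightly slower recruitment or a short delay for current users.
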